6.6 Dietary Restrictions

There are no dietary restrictions on this study. Patients should maintain a normal diet unless modifications are required to manage an AE such as diarrhea, nausea or vomiting.

6.7 Pregnancy/Contraception

6.7.1 Contraception

Pembrolizumab and vactosertib may have adverse effects on a fetus in utero. Furthermore, it is not known if pembrolizumab has transient adverse effects on the composition of sperm.

Patients should be informed that taking the study medication may involve unknown risks to the fetus (unborn baby) if pregnancy were to occur during the study. In order to participate in the study, patients of childbearing potential must adhere to the contraception requirement from the time of screening throughout the total duration of the drug treatment and the drug washout period. If there is any question that a patient of childbearing potential will not reliably comply with the requirements for contraception, that patient should not be entered into the study.

For this trial, male patients will be considered to be of non-reproductive potential if they have azoospermia (whether due to having had a vasectomy or due to an underlying medical condition).

Female patients will be considered of non-reproductive potential if they are either:

(1) Postmenopausal (defined as at least 12 months with no menses without an alternative medical cause; in women <45 years of age a high follicle stimulating hormone (FSH) level in the postmenopausal range may be used to confirm a post-menopausal state in women not using hormonal contraception or hormonal replacement therapy. In the absence of 12 months of amenorrhea, a single FSH measurement is insufficient.);

OR

(2) Have had a hysterectomy and/or bilateral oophorectomy, bilateral salpingectomy or bilateral tubal ligation/occlusion, at least 6 weeks prior to screening;

OR

(3) has a congenital or acquired condition that prevents childbearing.

Those who, in the opinion of the investigator, are sexually active and at risk for pregnancy, must agree to use highly effective contraception throughout the study and continue for at least 90 days after the last dose of vactosertib or 120 days after the last dose of pembrolizumab, whichever is later. Female and male patients of reproductive potential must agree to avoid becoming pregnant or impregnating a partner, respectively, by complying with one of the following effective contraception methods:

(1) Practice abstinence[†] from heterosexual activity;

OR

(2) Use (or have their partner use) acceptable contraception during heterosexual activity.

Acceptable methods of contraception are[‡]:

Single method (one of the following is acceptable):

- intrauterine device (IUD)

- vasectomy of a female patient's male partner
- contraceptive rod implanted into the skin

Combination method (requires use of two of the following):

- diaphragm with spermicide (cannot be used in conjunction with cervical cap/spermicide)
- cervical cap with spermicide (nulliparous women only)
- contraceptive sponge (nulliparous women only)
- male condom or female condom (cannot be used together)
- hormonal contraceptive: oral contraceptive pill (estrogen/progestin pill or progestin-only pill), contraceptive skin patch, vaginal contraceptive ring, or subcutaneous contraceptive injection

†Abstinence (relative to heterosexual activity) can be used as the sole method of contraception if it is consistently employed as the patient's preferred and usual lifestyle and if considered acceptable by local regulatory agencies and IRBs/ERCs. Periodic abstinence (e.g., calendar, ovulation, sympto-thermal, post-ovulation methods, etc.) and withdrawal are not acceptable methods of contraception.

‡If a contraceptive method listed above is restricted by local regulations/guidelines, then it does not qualify as an acceptable method of contraception for patients participating at sites in this country/region.

Patients should be informed that taking the study medication may involve unknown risks to the fetus (unborn baby) if pregnancy were to occur during the study. In order to participate in the study, patients of childbearing potential must adhere to the contraception requirements from the day of study medication initiation (or 14 days prior to the initiation of study medication for oral contraception) throughout the study period up to 120 days after the last dose of study medication. If there is any question that a patient of childbearing potential will not reliably comply with the requirements for contraception, that patient should not be entered into the study.

6.7.2 Use in Pregnancy

If a patient inadvertently becomes pregnant while on pembrolizumab-based treatment, the patient will be immediately discontinued from study treatment. The site will contact the patient at least monthly and document the patient's status until the pregnancy has been completed or terminated. The outcome of the pregnancy will be reported to Merck without delay and within 24 hours if the outcome is a SAE (e.g., death, abortion, congenital anomaly, or other disabling or life-threatening complication to the mother or newborn). The study Investigator will make every effort to obtain permission to follow the outcome of the pregnancy and report the condition of the fetus or newborn to Merck. If a male patient impregnates his female partner, the study personnel at the site must be informed immediately and the pregnancy must be reported to Merck and followed as described in Section 7.5.

6.7.3 Use in Nursing Women

It is unknown whether pembrolizumab and vactosertib is excreted in human milk. Since many drugs are excreted in human milk, and because of the potential for serious adverse reactions in the nursing infant, patients who are breast-feeding are not eligible for enrollment.

6.7.4 Pregnancy Tests

All women who are being considered for participation in the trial, and who are not surgically sterilized or postmenopausal, must be tested for pregnancy within 72 hours of each cycle of trial treatment and 30 days post treatment. If a urine test is positive or not evaluable a serum test will be required. Patients must be excluded/discontinued from the study in the event of a positive or borderline-positive test result.

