6.1.6 Optional Adjuvant Treatment

6.1.6.1 Pre-treatment

Participants interested in participating in the optional adjuvant treatment cohort (pembrolizumab + vactosertib) will complete the pre-treatment procedures 2 weeks (± 7 days) after surgery.

Study procedures and assessments:

- Informed consent for adjuvant treatment
- Review of eligibility (per the investigator's discretion). The rationale for enrolling (or not enrolling) participants in adjuvant therapy will be recorded, along with any supporting test results (e.g., circulating tumor DNA analysis).
- Concomitant medications
- Evaluation of AEs
- Directed physical examination
- Vital sign measurements and weight
- ECOG Performance status
- Serum or urine pregnancy test within 72 hours prior to the start of adjuvant treatment
- PT/INR and aPTT
- Hematology (other than CDC with diff), CBC with differential and platelet count

- Comprehensive serum chemistry (see Table 12)
- Urinalysis
- T3 (free and total), FT4 and TSH

Participants who are ineligible for the adjuvant treatment cohort will be followed every 90 days (Q90D; \pm 14 days) for up to 2 years post-surgery per Table 10 and section 6.1.7.

6.1.6.2 Cycle 1 through Cycle 8

Eligible participants will receive adjuvant treatment 6 weeks (\pm 2 weeks) after hepatic metastasectomy. Participants will receive adjuvant pembrolizumab + vactosertib for up to eight, 6-week cycles (approximately 1 year) or until disease recurrence is radiographically documented, unacceptable AE(s), intercurrent illness that prevents further administration of treatment, investigator's decision to discontinue the patient, administrative reasons requiring cessation of treatment, or withdrawal of consent, whichever occurs first.

Perform the following procedures and assessments on day 1 of each cycle unless specified otherwise:

- Concomitant medications
- Evaluation of AEs
- Directed physical examination
- Vital sign measurements and weight
- ECOG Performance status
- Hematology (other than CBC with diff), CBC with differential and platelet count*
- Comprehensive serum chemistry (see Table 12)*
- Urinalysis*
- T3 (free and total), FT4 and TSH*
- ECHO - perform at cycle 2 only
- Tumor Marker: CEA
- Tumor imaging with IV contrast to monitor disease status - perform every 12 weeks (i.e., day 1 of every other cycle)
- Correlative studies blood collection - perform every 12 weeks (i.e., day 1 of every other cycle)
- Pembrolizumab administration (see section 5.1)

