6.1.6.4 Safety Follow-up Visit

For patients receiving adjuvant treatment with pembrolizumab and vactosertib, the mandatory *Safety Follow-Up Visit* should be conducted approximately 30 days (+7 days) after the last dose of study treatment or before the initiation of a new anticancer treatment, whichever comes first.

Procedures and assessments:

- Concomitant medications
- Evaluation of AEs

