6.2 Trial Flow Chart

Table 10 Main Trial Flow Chart

Trial Period: Treatment Cycle/Visit:	Screening	Preoperative Treatment	Pre-Surgery	Surgery	Post-Surgery Safety F/U	Follow Up Phase ^{a,m}
		C1D1				
Scheduling Window:	-28d to -1d	≥7d post-last chemotherapy	+7-14d post-C1D1	+7-14d post-C1D1, 28-42d post-last chemo	14d ±7d post-op	Q90D ±14d post-op for up to 2y
Directed Medical History	X					
Main Trial Study Informed Consent	X ^b					
Future Biomedical Research consent (optional)	X ^b					
Inclusion/Exclusion Criteria	X					
Demographics and Full Medical History, including MMR/MSI status	X				X ^c	
Prior and Concomitant Medication Review	X ^d	X	X	X	X	X ^k
History of Prior Treatments and residual toxicity to prior treatment	X					
Trial Treatment Administration ^j		X				
Dispense vactosertib supply		X				

Trial Period: Treatment Cycle/Visit:	Screening	Preoperative Treatment	Pre-Surgery	Surgery	Post-Surgery Safety F/U	Follow Up Phase ^{a,m}
		C1D1				
Scheduling Window:	-28d to -1d	≥7d post-last chemotherapy	+7-14d post-C1D1	+7-14d post-C1D1, 28-42d post-last chemo	14d ±7d post-op	Q90D ±14d post-op for up to 2y
Post-study anticancer therapy status						X ^k
Survival Status						X
Review Adverse Events		X	X		X	X ^k
Complete Physical Examination	X					
Directed Physical Examination		X	X		X	
Vital Signs and Weight	X	X	X		X	
ECOG Performance Status	X ⁱ	X	X		X	
Pregnancy Test – Urine or Serum	X					
PT/INR and aPTT	X ⁿ		X			
Hematology, CBC with Differential and platelet count	X ⁿ	X	X		X	X ^a
Comprehensive Serum Chemistry Panel (see Table 12)	X ⁿ	X	X		X	X ^a
Urinalysis	X	X	X		X	X ^a

Trial Period: Treatment Cycle/Visit:	Screening	Preoperative Treatment	Pre-Surgery	Surgery	Post-Surgery Safety F/U	Follow Up Phase ^{a,m}
		C1D1				
Scheduling Window:	-28d to -1d	≥7d post-last chemotherapy	+7-14d post-C1D1, 28-42d post-last chemo	+7-14d post-C1D1, 28-42d post-last chemo	14d ±7d post-op	Q90D ±14d post-op for up to 2y
T3 (free and total), FT4 and TSH	X	X	X		X	X ^a
Tumor Marker: CEA p.	X	X	X		X	
Hep B surf Ag, Hep B sur Ab, Hep B core Ab, Hep C RNA	X					
Echocardiogram (ECHO)	X					
Electrocardiogram (ECG)		X ⁱ				
Disease Status Assessment/ Measurable disease	X		X			X
Tumor Imaging ^h	X ^g					X
Archival Tissue Collection		X ^o				
Biopsy of Liver Metastasis	X				X ^e	
Hepatic metastasectomy				X		
Correlative Studies: Blood Collection		X	X		X	X ^k
Correlative Studies: Stool	X		X		(X)	

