Survival Status								X
Review Adverse Events	X	X	X	X	X	X	X	X
Directed Physical Examination	X	X	X	X	X	X		
Vital Signs and Weight	X	X	X	X	X	X		
ECOG Performance Status	X	X	X	X	X	X		

Trial Period:	Pre-Treatment	Adjuvant Treatment				Post-Treatment		
		C1 D1	C2 D1	C3 D1	C4-8 D1	End of TX	Safety F/U	Follow Up Phase ^g
Scheduling Window:	2w ±14d post-op	6w ±14d post-op	12w ±3d post-op	18w ±3d post-op	24w-48w ±3d post-op	At DC +7d	30d after DC +7d	D90D ±14d post-last pembro dose for 1y or post-surgery for 2y (whichever occurs last)
Pregnancy Test – Urine or Serum	X							
PT/INR and aPTT	X							
Hematology, CBC with Differential and Platelet Count	X	X ^c	X	X	X	X		X
Comprehensive Serum Chemistry Panel (see Table 12)	X	X ^c	X	X	X	X		X
Urinalysis	X	X ^c	X	X	X	X		X
T3, FT4 and TSH	X	X ^c	X	X	X	X		X
Tumor Marker: CEA		X		X	X	X		
ECHO			X			X ^d		
Correlative studies: Blood collection		X ^e		X ^e	X ^e			X

Abbreviations: aPTT = activated partial thromboplastin time; CBC = complete blood count; CEA = carcinoembryonic antigen; ECOG = Eastern Cooperative Oncology Group; FT4 = free thyroxine; GI = gastrointestinal; INR = international normalized ratio; LDH = lactate dehydrogenase; pembro = pembrolizumab; post-op = post-operation; PT = prothrombin time; T3 = triiodothyronine; TSH = thyroid stimulating hormone; DC = discontinuation; F/U = follow-up; TX = treatment; d = day(s); w = week(s); y = year(s).

- Enrollment of eligible patients in the optional adjuvant therapy arm will be based on criteria listed in Section 3.3 and per the investigator's discretion. The rationale for enrolling (or not enrolling) participants in adjuvant therapy will be recorded, along with any supporting test results (e.g., circulating tumor DNA analysis). Ineligible participants will be followed q90d ±14d post-surgery for up to 2y as outlined in Table 10 and section 6.1.7.
- Test within 72 hours prior to the start of adjuvant treatment
- Tests do not need to be repeated at adjuvant C1D1 treatment visit if they were performed within 14 days prior to C1D1.

- d. ECHO does not need to be repeated at the End of Treatment visit if it was performed within the past 12 weeks.
- e. Perform every 12 weeks (i.e., day 1 of every other cycle) during the adjuvant treatment period. For imaging, it will be reviewed to note no evidence of radiographic progression or malignancy as determined by the PI.

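### Section 6.7.4 requires a pregnancy test at every cycle and 30 days after treatment, but the visit schedules list only one test per treatment phase

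*Combined protocol and SAP*

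**What the plan says.** Section 6.7.4 sets the rule: women who are neither surgically sterilised nor postmenopausal "must be tested for pregnancy within 72 hours of each cycle of trial treatment and 30 days post treatment". A positive or borderline result means exclusion or discontinuation.

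The operational text schedules less:

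- **Neoadjuvant phase.** Section 6.1.1 lists one test, within 72 hours before study drug. In Table 10 the row "Pregnancy Test – Urine or Serum" is marked at screening only.
- **Adjuvant phase, before treatment.** Section 6.1.6.1 lists "Serum or urine pregnancy test within 72 hours prior to the start of adjuvant treatment". Table 11 marks the pre-treatment column only, and its footnote reads "Test within 72 hours prior to the start of adjuvant treatment".
- **Adjuvant Cycles 1 to 8.** Section 6.1.6.2 opens with "Perform the following procedures and assessments on day 1 of each cycle unless specified otherwise". The list that follows has no pregnancy test.
- **After adjuvant treatment.** The End of Treatment list (6.1.6.3) has none. The safety visit in 6.1.6.4 "should be conducted approximately 30 days (+7 days) after the last dose of study treatment", and lists only concomitant medications and adverse events.
- **Post-surgical visit and follow-up phase (6.1.5, 6.1.7).** No pregnancy test in either list.

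**The concern.** The rule and the schedules cannot both be followed as written. Sites work from the schedules: 6.9 refers them to Table 10 for laboratory timing, and 6.1.5 sends women interested in adjuvant treatment to Table 11 and 6.1.6.1. A site that follows those exactly departs from 6.7.4.

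Section 6.7.1 warns: "Pembrolizumab and vactosertib may have adverse effects on a fetus in utero". Section 6.7.2 requires immediate discontinuation in pregnancy. Contraception is mandatory and a test precedes each phase, so the exposed group is women of childbearing potential whose contraception fails during treatment. For them the charts prompt no check before re-dosing from Cycle 2 onward, which is also when vactosertib rises from once to twice daily if Cycle 1 was tolerated. Tests omitted by following the charts would also count as deviations from 6.7.4.

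**Working it through.** There is no stated figure to reproduce. The check is a count of required against charted tests, followed by a comparison of visit windows.

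**Is the gap a table-reading artefact?** No. The prose visit lists in 6.1.1 and 6.1.6.1 to 6.1.6.4 agree with the marks in Tables 10 and 11.

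**Count per woman.** Let k be the number of adjuvant cycles received (0 to 8). Assume one 30-day test, after her last treatment phase.

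- Required over the whole trial: 1 (neoadjuvant cycle) + k (adjuvant cycles) + 1 (30 days) = k + 2.
- Charted: 2 if k ≥ 1 (screening and pre-adjuvant), 1 if k = 0.

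| k | Required | Charted | Not charted |
|---|---|---|---|
| 0 | 2 | 1 | 1 |
| 1 | 3 | 2 | 1 |
| 2 | 4 | 2 | 2 |
| 3 | 5 | 2 | 3 |
| 8 | 10 | 2 | 8 |

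For the adjuvant phase alone, required is k + 1 and charted is 1. With k = 8 that is 9 against 1, and the 8 uncharted tests are 7 (Cycles 2 to 8) plus 1 (30 days). If 6.7.4 also means a 30-day test after the neoadjuvant cycle in women who continue, add 1 to the required count for k ≥ 1; with k = 8 it becomes 2 of 11.

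**Neoadjuvant-only women: does an existing visit fall at 30 days?** Table 10 puts surgery 7 to 14 days after C1D1 and the post-surgical visit 14 ± 7 days after surgery. That visit therefore falls from 7 + 7 = 14 to 14 + 21 = 35 days after C1D1. With five days on and two off, the last vactosertib dose is on about Day 12, which is 11 days after C1D1. Thirty days later is 11 + 30 = 41 days after C1D1, outside that range, and Table 10 sets no visit for that time.

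**A smaller point: where the pre-adjuvant test is listed.** Adjuvant C1D1 is 6 weeks ± 14 days after surgery, so post-operative days 28 to 56.

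- Under 6.1.6.1, participants "will complete the pre-treatment procedures 2 weeks (± 7 days) after surgery", so on days 7 to 21. The smallest gap to C1D1 is 28 − 21 = 7 days, or 168 hours, which exceeds 72.
- Table 11 gives the same visit a window of 2 weeks ± 14 days, so days 0 to 28. The smallest gap is 0, but 72 hours is met only with the visit on days 25 to 28 and C1D1 on days 28 to 31.

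A test done at the visit itself therefore misses its own limit under one window and meets it only at the edge of the other.

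**The case against.** The safeguard is in the protocol. Section 6.7.4 is mandatory and binds the site whatever the charts show; contraception is required through 120 days after treatment, and pregnancies are reportable for 120 days, or 30 days if new anticancer therapy begins. On this view the defect is an omission in copying. That narrows the consequence but does not remove it, because contraception and reporting do not replace a test before re-dosing.

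The pointer in 6.9 names Table 10 only, whose per-cycle count is right for the single neoadjuvant cycle. That is correct, so 6.9 alone does not show that sites would miss the Cycle 2 to 8 tests. Section 6.1.5, however, directs adjuvant participants to Table 11 and 6.1.6.1, and these contain no later test either.

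The strongest objection is that 6.7.4 may be the text in error. Inclusion criterion 10, 6.1.1, 6.1.6.1, both flow charts and the Table 12 footnote all describe a test at the start of treatment or of a phase, and none describes one at each cycle. The documents do not settle which was intended, and cutting 6.7.4 back would also restore consistency. Given the stated fetal risk and the discontinuation rule, bringing the charts up to the mandatory text is the safer direction.

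On the visit window, the test carries its own 72-hour limit, so a site can schedule it separately. That is fair, and the point stays minor.

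**Conclusion.** The inconsistency is real. Over a full adjuvant course 8 of 9 required tests are uncharted, and over the whole trial 8 of 10; a neoadjuvant-only woman has 1 of 2 uncharted. Shorter courses reduce the gap as tabulated. The counts rest on one 30-day test, after the last treatment phase.

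These are counts per woman, not trial-level impact. Planned enrolment is up to 19, adjuvant treatment is optional, and the documents do not say how many women of childbearing potential are expected, so the number affected is unknown and could be very small or zero. No endpoint, sample size, power or significance level is touched. This is a participant-safety and compliance matter that should be corrected.

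**What to change.** 1. In Table 11 and 6.1.6.2, add a pregnancy test for women of childbearing potential within 72 hours before Day 1 of each adjuvant cycle.
2. In Table 11 and 6.1.6.4, add one at the 30-day safety visit.
3. In Table 10, add a 30-day post-treatment test for women not entering adjuvant therapy.
4. State in 6.7.4 whether women who continue to adjuvant treatment also need a 30-day test after the neoadjuvant cycle.
5. Move the pre-adjuvant test to adjuvant C1D1, keeping the 72-hour limit, and give the pre-treatment visit one window in 6.1.6.1 and Table 11.

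If the sponsor intends less testing, 6.7.4 must be amended and the reason given.

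The cost is low. The tests are already required, and the Day 1 and 30-day safety visits already exist for adjuvant participants. Neoadjuvant-only women need one urine or serum test about 30 days after their last dose, which may mean one extra contact because Table 10 sets no visit at that time.

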6.8 Clinical Criteria for Early Trial Termination

Early trial termination will be the result of the criteria specified below:

1. Quality or quantity of data recording is inaccurate or incomplete
2. Poor adherence to protocol and regulatory requirements
3. Incidence or severity of adverse drug reaction in this or other studies indicates a potential health hazard to patients
4. Plans to modify or discontinue the development of the study drug

In the event of Merck's decision to no longer supply study drug, ample notification will be provided so that appropriate adjustments to patient treatment can be made.

6.9 Laboratory Procedures/Assessments

Details regarding specific laboratory procedures/assessments to be performed in this trial are provided below. The total amount of blood/tissue to be drawn/collected over the course of the trial (from pre-trial to post-trial visits), including approximate blood/tissue volumes drawn/collected by visit and by sample type per patient can be found in the laboratory manual.

Refer to the Trial Flow Chart (Table 10) for the schedule of laboratory assessments.

6.9.1 Laboratory Safety Evaluations (Hematology, Chemistry and Urinalysis)

Laboratory tests for hematology, chemistry, urinalysis, and others are specified in Table 12.

Table 12 Laboratory Tests

Hematology	Chemistry	Urinalysis	Other
Hematocrit	Albumin	Blood	Serum β -human chorionic gonadotropin†
Hemoglobin	Alkaline phosphatase	Glucose	

Phase 2, Pembrolizumab, Vactosertib

Hematology	Chemistry	Urinalysis	Other
Platelet count	Alanine aminotransferase (ALT)	Protein	PT (INR)
WBC (total and differential)	Aspartate aminotransferase (AST)	Specific gravity	aPTT
Red Blood Cell Count	Lactate dehydrogenase (LDH)	Microscopic exam (If abnormal)	Total triiodothyronine (T3)
Absolute Neutrophil Count	Carbon Dioxide ‡ (CO ₂ or bicarbonate)	results are noted	Free thyroxine (T4)
Absolute Lymphocyte Count	Creatinine	Urine pregnancy test †	Thyroid stimulating hormone (TSH)
	Uric Acid		CEA
	Calcium		Hepatitis B surface antigen (HBsAg)
	Chloride		Hepatitis B surface antibody (HBsAb)
	Fasting glucose		Hepatitis B core antibody (HBcAb)
	Phosphorus		Hepatitis C virus RNA
	Potassium		Blood for correlative science
	Sodium		
	Magnesium		
	Total Bilirubin		
	Direct Bilirubin (If total bilirubin is elevated above the upper limit of normal)		
	Total protein		
	Blood Urea Nitrogen		

Abbreviations: aPTT = activated partial thromboplastin time; INR = international normalized ratio; PT = prothrombin time; WBC = white blood cell.

† Perform on women of childbearing potential only. If urine pregnancy results cannot be confirmed as negative, a serum pregnancy test will be required within 72 hours prior to Day 1 of cycle 1.

‡ If considered standard of care in your region.

Screening hematology, chemistry and urinalysis laboratory tests should be performed within 10 days prior to treatment. Results must be reviewed by the investigator or qualified designee and found to be acceptable prior to dose of trial treatment. Unresolved abnormal laboratory values that are drug-related AEs should be followed until resolution. Laboratory tests do not need to be repeated after the end of treatment if laboratory results are within normal range.

7 Reporting and Documentation of Results

